#### **4.3.3 Criteria to Resume Treatment After Dose Delay**

Subjects will be permitted to resume therapy at the same dose level(s) following resolution of the AE to  $\leq$ Grade 1 or to baseline within 6 weeks after last dose, with the exception of subjects who meet criteria for permanent discontinuation as specified in [Section 4.3.5](#). Subjects who meet criteria for permanent discontinuation should receive no further study therapy. The following exceptions apply:

If the toxicity resolves to  $\leq$ Grade 1 or baseline  $>$  6 weeks after last dose but the subject does not otherwise meet the criteria for permanent discontinuation (see [Section 4.3.5](#)) and the Investigator believes that the subject is deriving clinical benefit, then the subject may be eligible to resume the study drug(s) following the approval of the BMS Medical Monitor.

Subjects with a Grade 4 drug-related amylase and/or lipase increase that is not associated with symptoms or clinical manifestations of pancreatitis can be restarted on therapy once the levels have recovered to Grade 3 or less, and after consultation with the BMS Medical Monitor.

Subjects with baseline Grade 1 AST, ALT, or total bilirubin who require dose delays for reasons other than a drug-related hepatic event may resume treatment in the presence of Grade 2 AST, ALT, or total bilirubin.

Subjects who require dose delays for drug-related elevations in AST, ALT, or total bilirubin may resume treatment when these values have returned to their baseline CTCAE Grade or normal, provided the criteria for permanent discontinuation are not met.

Subjects may resume treatment in the presence of Grade 2 fatigue.

Drug-related endocrinopathies adequately controlled with only physiologic HRT may resume treatment.

Troponin T or I elevations will require the participant to undergo a cardiac and safety evaluation. Following this evaluation, determination of further treatment will be based on the discussion with the BMS Medical Monitor or designee.

#### **4.3.4 Treatment Beyond Disease Progression**

Accumulating evidence indicates a minority of participants treated with immunotherapy may derive clinical benefit despite initial evidence of PD.

Participants treated with nivolumab and BMS-986016 or BMS-986213 will be permitted to continue treatment beyond initial RECIST v1.1-defined PD, assessed by the Investigator, as long as they meet the following criteria:

Investigator-assessed clinical benefit

Tolerance of study treatment

Stable performance status

Treatment beyond progression will not delay an imminent intervention to prevent serious complications of disease progression (eg, CNS metastases)

Subjects provide written informed consent prior to receiving additional study treatment. All other elements of the main consent including description of reasonably foreseeable risks or discomforts or other alternative treatment options will still apply.

A follow-up scan should be performed at the next scheduled imaging evaluation 8 weeks later (but no sooner than 4 weeks) to determine whether there has been a decrease in the tumor size or continued PD. The assessment of clinical benefit should be balanced by clinical judgment as to whether the participant is clinically deteriorating and unlikely to receive any benefit from continued treatment with nivolumab and BMS-986016 or BMS-986213.

If the investigator feels that the subject continues to achieve clinical benefit by continuing treatment beyond progression, the subject should remain on the trial and continue to receive monitoring according to the Schedule of Activities ([Table 5.1-2](#)).

**For the subjects who continue study therapy beyond progression, further progression is defined as an additional 10% increase in tumor burden with a minimum 5 mm absolute increase from time of initial PD. This includes an increase in the sum of diameters of all**

**target lesions and/or the diameters of new measurable lesions compared to the time of initial PD. Study treatment should be discontinued permanently upon documentation of further progression.**

New lesions are considered measurable at the time of initial progression if the longest diameter is at least 10 mm (except for pathological lymph nodes that must have a short axis of at least 15 mm). Any new lesion considered nonmeasurable at the time of initial progression may become measurable and therefore included in the tumor burden if the longest diameter increases to at least 10 mm (except for pathological lymph nodes that must have a short axis of at least 15 mm). In situations where the relative increase in total tumor burden by 10% is solely due to inclusion of new lesions that become measurable, these new lesions must demonstrate an absolute increase of at least 5 mm.

#### **4.3.5 Guidelines for Permanent Discontinuation**

Subjects meeting any of the following criteria will be required to permanently discontinue all study drug(s) (BMS-986016 in Part A and Part A1; BMS-986016 and nivolumab [BMS-936558] or BMS-986213 in Parts B, C, D, and E):

Any  $\geq$  Grade 2 drug-related uveitis, eye pain, or blurred vision that does not respond to topical therapy and does not improve to Grade 1 severity within the retreatment period OR requires systemic treatment

Any  $\geq$  Grade 3 nonskin, drug-related AE lasting  $> 7$  days or recurs, with the following exceptions for laboratory abnormalities, drug-related uveitis, pneumonitis, bronchospasm, hypersensitivity reactions, infusion reactions, and endocrinopathies

Any  $\geq$  Grade 3 drug-related myocarditis, uveitis, pneumonitis, bronchospasm, or hypersensitivity reaction of any duration requires discontinuation.

Any  $\geq$  Grade 3 infusion reaction that does not return to Grade 1 in 6 hours or less requires discontinuation.

Any  $\geq$  Grade 3 drug-related endocrinopathies adequately controlled with only physiologic HRT do not require discontinuation.

Any  $\geq$  Grade 3 drug-related laboratory abnormalities do not require treatment discontinuation except:

- Any  $\geq$  Grade 3 drug-related thrombocytopenia  $> 7$  days or associated with bleeding requires discontinuation.
- AST, ALT, or bilirubin abnormalities that meet DLT criteria ([Section 3.1.2.6](#)) (In most cases of AST or ALT elevation meeting DLT criteria, study drugs will be permanently discontinued. If the Investigator determines a possible favorable benefit-risk ratio that warrants continuation of study drugs, a discussion between the Investigator and the BMS Medical Monitor/designee must occur.)
- Elevated troponin that meets DLT criteria ([Section 3.1.2.6](#))

Any Grade 4 drug-related AE or laboratory abnormality (including, but not limited to, creatinine, AST, ALT, or total bilirubin), except for the following events, which do **not** require discontinuation:

- Grade 4 neutropenia  $\leq$  7 days
- Grade 4 lymphopenia or leukopenia
- Isolated Grade 4 amylase or lipase abnormalities that are not associated with symptoms or clinical manifestations of pancreatitis
- Isolated Grade 4 electrolyte imbalances/abnormalities that are not associated with clinical sequelae and are corrected with supplementation/appropriate management within 72 hours of their onset
- Grade 4 drug-related endocrinopathy AEs, such as adrenal insufficiency, adrenocorticotropic hormone deficiency, hyper- or hypothyroidism, or glucose intolerance, which resolve or are adequately controlled with physiologic HRT (corticosteroids, thyroid hormones) or glucose-controlling agents, respectively, may not require discontinuation after discussion with and approval from the BMS Medical Monitor.

Any event that leads to delay in dosing lasting  $>$  6 weeks from the previous dose requires discontinuation, with the following exceptions:

- Dosing delays to allow for prolonged steroid tapers to manage drug-related AEs are allowed. Prior to reinitiating treatment in a subject with a dosing delay lasting  $>$  6 weeks from the previous dose, the BMS Medical Monitor must be consulted. Tumor assessments should continue as per protocol even if dosing is delayed. Periodic study visits to assess safety and laboratory studies should also continue every 6 weeks or more frequently if clinically indicated during such dosing delays.
- Dosing delays lasting  $>$  6 weeks from the previous dose that occur for nondrug-related reasons may be allowed if approved by the BMS Medical Monitor. Prior to reinitiating treatment in a subject with a dosing delay lasting  $>$  6 weeks, the BMS Medical Monitor must be consulted. Tumor assessments should continue as per protocol even if dosing is delayed. Periodic study visits to assess safety and laboratory studies should also continue every 6 weeks or more frequently if clinically indicated during such dosing delays.

Any AE, laboratory abnormality, or intercurrent illness which, in the judgment of the Investigator, presents a substantial clinical risk to the subject with continued nivolumab dosing.

The consideration to reinitiate study therapy in selected cases at any time point after discontinuation could be made on a case-by-case basis after considering the overall benefit-risk profile and in consultation between the Investigator and the study Sponsor. The selected subjects will need to meet eligibility criteria. The original dose and schedule and protocol rules would apply accordingly ([Section 3.1.2.5](#)).

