### **Part D1 Safety Lead-in**

Given the theoretical risk of infusion reactions with the administration of the BMS-986213, a safety lead-in will be employed for the first (up to) 9 subjects enrolling into subpart D1 and prior to the start of randomization.

The lead-in will follow a 3 + 3 + 3 design to monitor any potential Grade 3 or 4 infusion reactions that may occur as a result of coadministration of both drugs. Three subjects will be treated in each cohort. There will be no time interval restrictions for patients to begin treatment within a cohort.

If 0 to 1 of the first 3 subjects experiences a Grade 3 or 4 infusion reaction, then the cohort will be expanded to 6 subjects. If 2 of 6 subjects experience a Grade 3 or 4 infusion reaction, the cohort will be expanded to 9 subjects. If  $\geq 2$  of 3,  $\geq 3$  of 6, or  $\geq 3$  of 9 subjects experience Grade 3 or 4 infusion reactions, then further treatments with BMS-986213 will be held until further evaluation can be performed and randomization to the 2 coadministration arms may commence. If no more than 1 of 6 subjects, or 2 of 9, experience a Grade 3 or 4 reaction, randomization across all 3 arms will commence.

The infusion reaction observation period will be 48 hours.

Subjects will be instructed to contact the site regarding any potential infusion reaction symptoms. All Grade 3 or 4 infusion reactions should be reported within 24 hours to the BMS Medical Monitor and reported as an SAE if it meets the criteria. Infusion reactions should be graded

according to NCI CTCAE v4.0 guidelines. Prior to allowing dosing of each subsequent cohort, sites will be contacted to confirm that there has been no report of serious reactions.

For the management of infusion reactions, please refer to the treatment guidelines outlined in [Section 3.4.4](#).

The above enrollment plan will be executed by setting enrollment/treatment caps for each cohort in IVRS.

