### **3.4.4 Treatment of BMS-986016, Nivolumab-related Infusion Reactions**

Since all study treatments contain only human immunoglobulin protein sequences, they are unlikely to be immunogenic and induce infusion or hypersensitivity reactions. However, if such a reaction were to occur, it might manifest with fever, chills, rigors, headache, rash, pruritus, arthralgias, hypotension, hypertension, bronchospasm, or other allergic-like reactions. All Grade 3 or 4 infusion reactions should be reported within 24 hours to the BMS Medical Monitor and reported as an SAE if it meets the criteria. Infusion reactions should be graded according to NCI CTCAE v4.0 guidelines.

If a subject has an infusion reaction with nivolumab, the BMS-986016 infusion can be given (without prophylactic medications) if the infusion reaction resolves within 3 hours. For scheduling purposes after a nivolumab infusion reaction, the BMS-986016 infusion may be given within the next 2 days. Prophylactic preinfusion medications should be given prior to all subsequent nivolumab infusions.

Treatment recommendations are provided below and may be modified based on local treatment standards and guidelines, as appropriate:

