**For Grade 1 symptoms (mild reaction; infusion interruption not indicated; intervention not indicated):**

Remain at bedside and monitor subject until recovery from symptoms. The following prophylactic premedications are recommended for future infusions: diphenhydramine 50 mg (or equivalent) and/or acetaminophen/paracetamol 325 to 1000 mg at least 30 minutes before additional study drug administrations.

**For Grade 2 symptoms (moderate reaction requires therapy or infusion interruption but responds promptly to symptomatic treatment [eg, antihistamines, nonsteroidal anti-inflammatory drugs, narcotics, corticosteroids, bronchodilators, IV fluids]; prophylactic medications indicated for ≤ 24 hours):**

Stop the infusion, begin an IV infusion of normal saline, and treat the subject with diphenhydramine 50 mg IV (or equivalent) and/or acetaminophen/paracetamol 325 to 1000 mg; remain at bedside and monitor subject until resolution of symptoms. Corticosteroid and/or bronchodilator therapy may also be administered as appropriate. If the infusion is interrupted, then restart the infusion at 50% of the original infusion rate when symptoms resolve; if no further complications ensue after 30 minutes, the rate may be increased to 100% of the original infusion rate. Monitor subject closely. If symptoms recur, then no further study drug will be administered at that visit.

For future infusions, the following prophylactic premedications are recommended:

Diphenhydramine 50 mg (or equivalent) and/or acetaminophen/paracetamol 325 to 1000 mg should be administered at least 30 minutes before study drug infusions. If necessary, corticosteroids (up to 25 mg of SoluCortef or equivalent) may be used.

**For Grade 3 or 4 symptoms (severe reaction, Grade 3: prolonged [ie, not rapidly responsive to symptomatic medication and/or brief interruption of infusion]; recurrence of symptoms following initial improvement; hospitalization indicated for other clinical sequelae [eg, renal impairment, pulmonary infiltrates]; life-threatening, Grade 4: pressor or ventilatory support indicated):**

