Immediately discontinue infusion of study drug. Begin an IV infusion of normal saline and treat the subject as follows: Recommend bronchodilators, epinephrine 0.2 to 1 mg of a 1:1000 solution for subcutaneous administration or 0.1 to 0.25 mg of a 1:10,000 solution injected slowly for IV administration, and/or diphenhydramine 50 mg IV with methylprednisolone 100 mg IV (or equivalent), as needed. Subject should be monitored until the Investigator is comfortable that the symptoms will not recur. All study drug(s) will be permanently discontinued. Investigators should follow their institutional guidelines for the treatment of anaphylaxis. Remain at bedside and monitor subject until recovery of the symptoms.

In case of late-occurring hypersensitivity symptoms (eg, appearance of a localized or generalized pruritus within 1 week after treatment), symptomatic treatment may be given (eg, oral antihistamine or corticosteroids).

Please refer to [Appendix 4](#) for a complete list of the AE management algorithms.

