### **3.5 Discontinuation of Subjects From Treatment**

Subjects MUST discontinue investigational product (and noninvestigational product at the discretion of the Investigator) for any of the following reasons:

Subject's request to stop study treatment

Pregnancy

Termination of the study by BMS

Loss of ability to freely provide consent through imprisonment or involuntarily incarceration for treatment of either a psychiatric or physical (eg, infectious disease) illness

Inability to comply with protocol requirements

- Progressive disease (see also [Section 4.3.4](#) for details regarding continuing treatment beyond initial assessment of PD per RECIST)

Clinical deterioration as assessed by the Investigator

Adverse event meeting discontinuation criteria ([Section 4.3.5](#))

All subjects who discontinue investigational product should comply with protocol-specified follow-up procedures as outlined in [Section 5](#). The only exception to this requirement is when a subject withdraws consent for all study procedures, including post-treatment study follow-up, or loses the ability to consent freely (ie, is imprisoned or involuntarily incarcerated for the treatment of either a psychiatric or physical illness).

If study treatment is discontinued prior to the subject's completion of the study, the reason for the discontinuation must be documented in the subject's medical records and entered on the appropriate case report form (CRF) page.

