##### **4.3.2 Dose Delay Criteria**

In some cases, the natural history of select AEs associated with immunotherapy can differ from and be more severe than AEs caused by other therapeutic classes. Early recognition and management may mitigate severe toxicity.

Guidance for Investigators is provided in the current BMS-986016 and BMS-936558 (nivolumab) IBs. Additionally, management algorithms have been developed to assist Investigators with select toxicities and can be found in the current BMS-936558 (nivolumab) IB; toxicities for which management algorithms have been developed include:

Pulmonary

Gastrointestinal

Hepatic

Endocrine

Renal

Dermatologic

Neurologic (see [Table 5.1-2](#) “Neurological Exam” for criteria for protocol-required neurologic exams)

Cardiac

Subjects who experience the following must have all study drug(s) held:

Potential DLTs (per definition, are related to study drug) until DLT relatedness is defined

Select drug-related AEs and drug-related laboratory abnormalities:

- $\geq$  Grade 1 pneumonitis
- $\geq$  Grade 1 myocarditis (see [Appendix 4](#))
- All troponin T or I elevations require a dose delay to allow for prompt cardiac and safety evaluation.
- $\geq$  Single grade increase shift from baseline (at least to Grade 2) of AST, ALT, and/or total bilirubin
- $\geq$  Grade 2 creatinine
- $\geq$  Grade 2 diarrhea or colitis
- $\geq$  Grade 2 neurological AE
- Grade 4 amylase and/or lipase abnormalities regardless of symptoms or clinical manifestations

AE, laboratory abnormality, or concurrent illness that, in the judgment of the Investigator, warrants delaying the dose of study drug.

Subjects may be dosed no less than 12 days in Q2W regimen and 25 days in Q4W from the previous dose and no more than 3 days from scheduled dose. If an infusion cannot be administered at a scheduled visit, it should be administered as soon as possible. Subsequent dosing visits will follow every 2 weeks or every 4 weeks after the delayed dose. A dose given more than 3 days after the intended dose date will be considered a delay. A maximum delay of 6 weeks between doses is allowed. Longer delays may be allowed following discussion with the Medical Monitor. Subjects who meet criteria listed in [Section 4.3.5](#) are required to permanently discontinue all study drug(s). All other subjects will be permitted to resume therapy with study drug(s) at the same dose level(s) following resolution of the AE as described in Section 4.3.3.

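### For a Grade 3 infusion reaction that is back to Grade 1 within 6 hours and is not classed as hypersensitivity or bronchospasm, Section 3.4.4 ends treatment while Sections 4.3.5 and 4.3.2 allow it to resume, and nothing says which governs

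*Combined protocol and SAP*

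**What the plan says.** Three current sections bear on whether study drug continues after a severe infusion reaction.

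- **Section 3.4.4** (treatment of infusion reactions) handles the two highest grades in one block, which opens "For Grade 3 or 4 symptoms (severe reaction, Grade 3: prolonged". Within that block it says "All study drug(s) will be permanently discontinued". No time to resolution is attached.
- **Section 4.3.5** (permanent discontinuation) has a general rule for drug-related non-skin events of Grade 3 or higher that last more than 7 days or recur. Its list of exceptions includes "bronchospasm, hypersensitivity reactions, infusion reactions, and endocrinopathies". Infusion reactions of Grade 3 or higher then get their own line: "Grade 3 infusion reaction that does not return to Grade 1 in 6 hours or less requires discontinuation".
- **Section 4.3.2** (dose delay) sends subjects who meet Section 4.3.5 to permanent discontinuation and then says "All other subjects will be permitted to resume therapy with study drug(s) at the same dose level(s) following resolution of the AE". Section 4.3.3 likewise makes Section 4.3.5 the bar to resuming.

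The cross-references diverge. Section 3.5 lists "Adverse event meeting discontinuation criteria" as a reason to stop and cites Section 4.3.5. The Part D1 safety lead-in in Section 3.1.2.5 says "For the management of infusion reactions, please refer to the treatment guidelines outlined in" Section 3.4.4.

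**The concern.** A site that looks up the reaction in Section 3.4.4 is told to end treatment. A site that looks it up in Section 4.3.5, which Section 3.5 names as the source of adverse-event stopping criteria, finds that stopping is not mandatory once the reaction has settled within 6 hours, and Section 4.3.2 then permits the next dose at the same level. Two sites could treat the same event in opposite ways and each cite the protocol.

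The decision is whether to re-expose a subject after a severe reaction, so the first stake is safety. The second is consistent conduct. Section 3.1.2.4 makes rechallenge conditional on there having been no relatlimab-related adverse event that led to permanent discontinuation, so the rule a site applied can also decide whether a subject is eligible for rechallenge.

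**Working it through.** The main check is a comparison of texts. The protocol states no figure for this event.

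**1. Apply both rules to each type of event.**

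| Event | Section 3.4.4 | Sections 4.3.5 and 4.3.2 | Conflict? |
|---|---|---|---|
| Grade 3, not back to Grade 1 within 6 hours | Stop | Stop (6-hour line) | No |
| Grade 3, back to Grade 1 within 6 hours, classed as drug-related hypersensitivity or bronchospasm | Stop | Stop (any duration) | No |
| Grade 3, back to Grade 1 within 6 hours, not so classed | Stop | Stopping not required; may resume | **Yes** |
| Grade 4, drug-related | Stop | Stop (Grade 4 rule; infusion reactions are not among its exceptions) | No |

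One row conflicts. In that row the outcome also depends on whether the event is labelled an infusion reaction or a hypersensitivity reaction.

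**2. Look for a tie-breaker.** Neither 3.4.4 nor 4.3.5 cites the other on this point or claims precedence. Appendix 4, to which 3.4.4 refers, has no algorithm titled for infusion reactions.

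**3. Part D1 lead-in.** Section 3.1.2.5 counts subjects with a Grade 3 or 4 infusion reaction. A subject who has had one is already counted, whatever is decided about later doses. The observation period is 48 hours, and Section 4.3.2 puts the next Q4W dose at least 25 days (25 × 24 = 600 hours) after the previous one.

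**4. Part D1-Q4W primary endpoint.** Section 8.3.1 defines it as subjects with at least one Broad Scope SMQ event within 2 days after any infusion, divided by treated subjects. A subject whose first reaction codes to a listed term is already in the numerator, and re-dosing adds nothing. Infusion-related reaction is not itself a term in the Appendix 5 list (MedDRA 18.0), so re-dosing could in principle produce a subject's first counted event.

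For scale, reproduce the plan's precision at 14% in each arm of 75: 1.96 × √(2 × 0.14 × 0.86 / 75) = 0.111, which matches the stated ±11.1%. One subject changing status moves an arm's rate by 1/75 = 1.3 percentage points.

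**5. Frequency.** Section 1.4.1.4.2 (cutoff 18-Jun-2018, three studies) lists 20 Grade 1 and 31 Grade 2 infusion-related reactions among 876 combination-treated subjects. That is 51 reactions, with none of Grade 3 listed. Section 1.5 reports 5 monotherapy infusion-related reactions, all Grade 1 or 2, and separately a Grade 3 allergic reaction.

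**The case against.** The strongest reply is that a site can comply with everything by stopping. Section 4.3.5 says when stopping is mandatory, and Section 4.3.2 only permits resumption, so stopping under 3.4.4 breaches neither. That is true, but it does not work in the other direction: a site that uses the permission in 4.3.2 breaches 3.4.4. If 3.4.4 always prevails, the 6-hour condition has no effect, which is hard to square with its having been written.

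Second, 3.4.4 is introduced by "Treatment recommendations are provided below and may be modified based on local treatment standards and guidelines, as appropriate". That wording concerns treatment recommendations, while the discontinuation sentence is phrased as an instruction. If local modification did extend to it, sites would still differ.

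Third, 3.4.4 describes Grade 3 as prolonged, recurrent after improvement or needing hospitalization. This may make resolution within 6 hours less usual, but it does not exclude it, and 4.3.5 presupposes such cases.

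Fourth, there are central controls, and these stand. Grade 3 and 4 infusion reactions should reach the Medical Monitor within 24 hours. A drug-related one falls within the DLT definition in Section 3.1.3, and potential DLTs require study drug to be held pending evaluation. A reader might infer that re-exposure happens without the sponsor's knowledge; the documents do not support that. But none of these controls says which rule the evaluation must apply. Section 4.3.5 also allows case-by-case reinitiation after discontinuation, in consultation with the sponsor. Ordinary resumption under 4.3.2 does not call for that step, so the conflict still matters.

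**Conclusion.** The contradiction is real, lies in current text and is narrow: Grade 3, back to Grade 1 within 6 hours, not classed as hypersensitivity or bronchospasm. It matters for safety and uniform conduct, not for the trial's inferences.

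Several stronger readings are not supported:

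- A reader might infer that Grade 4 reactions are also in dispute. Drug-related Grade 4 reactions are stopped under both rules.
- A reader might infer that the lead-in decision on the fixed-dose combination is affected. Its count is fixed by the first qualifying reaction.
- A reader might infer that unequal re-dosing distorts the Part D1-Q4W endpoint by changing the number of infusions at risk. The endpoint is per subject, so the effect is at most small, through subjects whose first reaction fell outside the SMQ.
- A reader might put the size at none re-treated under one rule and all under the other. That describes what the rules allow, not how often the event occurs.

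The documents give no frequency for the conflicting case. That it is uncommon is inferred from the 2018 safety summary not listing any Grade 3 infusion-related reaction, which is not the same as a reported zero. Appendix 7 records that enrollment closed on 30-Jul-2021, so the remaining exposure is in subjects still on treatment, which Section 3.1 allows beyond 5 years, and in those still eligible for rechallenge.

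**What to change.** The sponsor should reconcile Sections 3.4.4, 4.3.5 and 4.3.2 so that one discontinuation rule covers a Grade 3 infusion reaction that resolves within 6 hours, and add cross-references between the sections. The Part D1 lead-in needs no rule of its own, because its pointer to 3.4.4 will then lead to the reconciled text. The same edit could state how an event that might be labelled either infusion reaction or hypersensitivity is to be classified, since 4.3.5 treats the two differently. Which rule is right is a clinical decision for the sponsor.

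The cost is a few sentences of protocol wording and notice to sites with subjects still on treatment or eligible for rechallenge. No sample size, endpoint or analysis changes.
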